9.2 Statistical Methods

9.2.1 Overview of Statistical Analysis

Descriptive statistics will be performed separately for the early and late access treatment groups. The estimated patency rates will be calculated using the SVS reporting standards guidelines.³¹ Should there be considerable site differences and with sufficient number of patients within sites, stratified and/or weighted estimates may be performed.

9.2.2 Estimating primary effectiveness and primary safety endpoints

The percentage of patients with primary effectiveness success rates as defined in section 4 will be reported by randomized groups. The 95% confidence interval (CI) calculated using the Clopper-Pearson² exact method for binomial data will be reported by randomized groups. No formal statistical testing of the differences in primary effectiveness rates by randomized groups will be performed.

Similarly, the percentage of patients with MACE together with its 95% CI calculated using the Clopper-Pearson exact method will be reported by randomized groups. The number and percentage of patients in each of the MACE components will also be reported by randomized groups.

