| Patient Number | A total of 50 patients will be randomized to early access, successfully provided early cannulation within 72 hours, and will be followed to 6 months, to provide the data required for submission to the FDA. A 12month assessment for unexpected complications will also be obtained for early access subjects. Patients randomized to the early access group who are not cannulated in the <72-hour period will be followed as a late-access subject |

Artegraft, Inc.
Protocol: ARTCT.BEACH.001

Version 4.0 CONFIDENTIAL 21June2019 Page 9 of 81

| | for 30 days after first cannulation. It is estimated that up to 10 additional patients may fall into this category. A total of 25 patients will be randomized to late access, cannulated at 10 days or later after implant and followed for at least 30 days after first cannulation [Day 0] to assess perioperative major adverse clinical events (MACE) rates and patency data. The late access group will also be assessed for patency at 6 months through a telephone interview or office visit to provide a more robust data set |
|---|---|
| Intervention Description | Patients will be implanted with the Artegraft, for vascular cannulation for hemodialysis, using standard vascular techniques, according to the Instructions for Use. |
| Number of Investigators and Study Centers | Up to five (5) investigational sites are expected to participate in the trial. |
| Study Duration | The enrollment goal is ≥3 patients per site, per month. The anticipated enrollment period is 6 months; the patient enrollment duration for early-access patients is a minimum of 6 months, and total study duration is expected to be 12 months. |
| | The follow-up period on the early access patients will be 6 months and 30 days on the late access patients. In addition, a follow-up telephone call, based on a questionnaire, will be made to the early access patients and/or dialysis centers to determine if any unexpected complications had occurred during the 6-12-month period. For this reason, all patients will be consented to 12 months. The late access group will also be assessed for patency at 6 months through a telephone interview or office visit to provide a more robust data set. |
| Primary Effectiveness Endpoint | Early access success, defined by three cannulations, the first one started within 72 hours after implantation, all with minimum dialysis flow rates of 250 ml/min pump flow rate, with a minimum 17-gauge needle. |

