- 13. History or evidence of severe peripheral arterial disease in the extremity selected for implant (i.e. arterial inflow insufficient to support hemodialysis)
- 14. History of cancer with active disease or treatment within the previous year, except for non-invasive basal or squamous cell carcinoma of the skin
- 15. Bleeding diathesis, other than that associated with ESRD
- 16. Scheduled renal transplant within 6 months
- 17. Patients who require chronic anticoagulation except for antiplatelet therapy. Patients currently receiving or who have received within the last month direct thrombin inhibitors, factor Xa inhibitors, or vitamin K antagonists should not be included in the study.

Artegraft, Inc.
Protocol: ARTCT.BEACH.001

Data Populations

All patients who receive an Artegraft implant will be included in the safety and performance analyses for the device.

The early-access group is composed of the 50 patients that are enrolled, implanted with the Artegraft, successfully provided the first cannulation within 72 hours, and are followed to 6 months. This early-access population will be used to assess Primary, Assisted Primary, and Secondary Patency at 4, 12, and 26 weeks. This early-access population also will be used to assess perioperative major adverse clinical events (MACE) rates, and all adverse events to 26 weeks.

The late-access group is composed of 25 patients that are enrolled, implanted with the Artegraft, that are first accessed at >/= 10 days, and that are followed to 30 days post Day 0. This group will be used to assess perioperative major adverse clinical events (MACE) rates and primary, assisted primary, and secondary patency, at 30 days post Day 0. The late access group will also be assessed for patency at 6 months through a telephone interview or office visit to provide a more robust data set.

Table 1a: Schedule of Assessments (SoA) Early Access Patients

| Procedure | Screening Day -45 to Day of Surgery | Day 0 [1st successful cannulation] (May occur on day of surgery) | Day 1 – 17 Days post Day 0 | Day 30 +/- 3 days post Day 0 | 12 weeks +/- 7 days post day 0 | 6 Months +/- 7 days post day 0 | 12 Months +/- 14 days post day 0* Extended Follow-up |
|--|--|---|--|--|---|---|--|
| Eligibility (inclusion/exclusion) | Х | | | | | | |
| Informed Consent | Х | | | | | | |
| Medical History | Х | | | | | | |
| Prior and concomitant medication | Х | | Х | Х | Х | Х | |
| Physical Exam | Х | | Х | Х | Х | Х | |

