| 12-Lead ECG, when medically indicated | X | | | | | | |
| Vessel mapping (if not done within 8 weeks) | Х | | | | | | |
| Pregnancy test: serum (Women of child-bearing potential only; to be assessed within 7 days of implant) | Х | | | | | | |
| Hematology and coagulation lab test | Х | | | | | | |
| Surgical implant of Artegraft | Х | | | | | | |
| Documentation of surgical procedure | X | | | | | | |
| Assessment of wound healing | | Х | Х | Х | Х | Х | |
| Graft Patency Assessment | Х | Х | Х | Х | Х | Х | Х |
| Adverse event assessment | Х | Х | Х | Х | Х | Х | X ⁺ |
| Medical Device malfunctions | Х | Х | Х | Х | Х | Х | |
| Documentation of graft interventions | X | Х | Х | Х | Х | Х | |
| Use of Dialysis Catheter | | Х | Х | Х | Х | Х | |

These patients will be having dialysis every few days – assessments should be the same or similar at each post-implant visit.

^{*} Extended follow-up will be assessed for patency and AEs only via a telephone follow-up or office visit

⁺ AEs between 6 months and 12 months.

Table 2b: Schedule of Assessments (SoA) Late Access and Early Access Drop-outs

| Procedure | Screening Day -45 to Day of Surgery | Day 0 [1st successful cannulation] (May occur on day of surgery) | Day 1 – 17 Days post Day 0 | Day 30 +/- 3 days post Day 0 | 6 Months +/- 7 days post day 0* Extended Duration Follow-up |
|--|--|---|----------------------------------|--|---|
| Eligibility (inclusion/exclusion) | Х | | | | |
| Informed Consent | Х | | | | |
| Medical History | Х | | | | |
| Prior and concomitant medication | Х | | Х | Х | |
| Physical Exam | Х | | X | Х | |
| 12-Lead ECG, when medically indicated | Х | | | | |
| Vessel mapping (if not done within 8 weeks) | Х | | | | |
| Pregnancy test: serum (Women of child-bearing potential only; to be assessed within 7 days of implant) | X | | | | |
| Hematology and coagulation lab test | Х | | | | |
| Surgical implant of Artegraft | Х | | | | |
| Documentation of surgical procedure | Х | | | | |
| Assessment of wound healing | | Х | Х | Х | |
| Graft Patency Assessment | Х | Х | Х | Х | Х |
| Adverse event assessment | Х | Х | Х | Х | X ⁺ |
| Medical Device malfunctions | Х | Х | Х | Х | |
| Documentation of graft interventions | Х | Х | Х | Х | |
| Use of Dialysis Catheter | | Х | Х | Х | |

These patients will be having dialysis every few days – assessments should be the same or similar at each post-implant visit.

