4.0 OBJECTIVES AND ENDPOINTS

Table 6: Study Objectives and Endpoints

| able 0. Study Objectives and Endpoints | | | | |
|---|---|--|--|--|
| Study Objective | The objective of the BEACH Trial is to demonstrate that early access of Artegraft is associated with acceptable rates of successful early access, and acceptable rates of a composite of adverse events, to support a modification of existing device labeling stating that Artegraft is capable of cannulation within 72 hours post implantation. | | | |
| Primary Effectiveness Endpoint | Early access success, defined by three cannulations, the first one started within 72 hours post implantation, all with minimum dialysis flow rates of 250 ml/min pump flow rate, with a minimum 17-guage needle. | | | |
| | Expectations: $^{\sim}80\%$ of patients in the early access group will have first cannulation within 72 hours. | | | |
| | Expectations: ~90% of patients receiving early access will have 3 successful cannulations. | | | |
| Primary Safety Endpoint | A composite of major adverse clinical events (MACE) including perigraft infection, hemorrhage, thrombosis, steal syndrome, and pseudoaneurysm within 30 days after first cannulation [Day 0] in the early-access and late-access groups. | | | |
| | Expectation: ~20% of patients will have at least one MACE event; no significant difference in event number or type between early and late access groups. | | | |
| | All MACE will be adjudicated by an independent accessor. | | | |
| Secondary Effectiveness Endpoints | Patency (Primary, Assisted Primary, and Secondary) at 30 days after first successful cannulation [Day 0], and at 12 weeks and 6 months after implantation in the early-access group and at 30 days post-Day 0 in the lateaccess group. The late access group will also be assessed for patency at 6 months through a telephone interview or office visit to provide a more robust data set. | | | |
| | Expectations: | | | |
| | Patency rates [all 3 types] at 30 days will be similar in the early and late access groups. | | | |
| | We expect primary patency to be ≥85%, ≥75% and ≥65% at 30 days, 3 months, and 6 months, respectively. | | | |
| | Primary-assisted patency rates at 30 days, 3 months, and 6 months will be ≥85%. | | | |
| | Secondary patency rates will be ≥90% and ≥90% at 3 and 6 months, respectively. | | | |

Artegraft, Inc.
Protocol: ARTCT.BEACH.001

Version 4.0 CONFIDENTIAL 21June2019 Page 29 of 81

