9.0 STATISTICAL PLAN

9.1 Sample Size Determination

The sample size for this study is logistically rather than statistically driven.

A total of 50 patients will be enrolled, randomized and successfully provided early cannulation within 72 hours, and followed to 6 months. Another group of 25 patients will be randomly assigned and provided cannulation for 10 or more days after implant and followed only to 30 days to assess perioperative MACE rates. No loss to follow-up is projected at 30-days post implantation.

Previously published patency data (refer to the background section above) will be used at 12 weeks and 6 months for clinical context. The early access study group results will be compared with these previously published data, which were reported for Artegraft normal cannulation times. It should be noted that complications may or may not result in an early access failure. Confidence intervals will be presented around each endpoint. The observed rates will be numerically compared with the expected rates and no formal statistical hypothesis will be tested.

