9.2.7 Safety

The safety analysis population will include a subset of patients in the screened analysis population who are implanted with the Artegraft, regardless of whether randomized early or late vascular access is performed. The safety analysis population will be used in reporting safety and product use characteristics.

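### Section 4 expects no significant between-arm difference in 30-day MACE, but Section 9 plans no between-arm estimate, and the early-access MACE population is defined in two ways

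*Combined protocol and SAP*

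**What the plan says.** Section 4 gives two expectations for MACE within 30 days of first cannulation (Day 0): about 20% of patients with at least one event, and "no significant difference in event number or type between early and late access groups".

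Section 9 is descriptive. Section 9.1 calls the sample size logistical and adds: "The observed rates will be numerically compared with the expected rates and no formal statistical hypothesis will be tested". Section 9.2.1 says: "Descriptive statistics will be performed separately for the early and late access treatment groups". Section 9.2.2 is specific to MACE: "Similarly, the percentage of patients with MACE together with its 95% CI calculated using the Clopper-Pearson exact method will be reported by randomized groups". It also promises component counts by randomised group.

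On who is counted, Section 9.2.7 defines the safety population as implanted patients "regardless of whether randomized early or late vascular access is performed", and Section 10.2.8 uses that set for all safety analyses. Data Populations in Section 1.0 first includes every implanted patient. It then defines the early-access group as the 50 first cannulated within 72 hours and continues: "This early-access population also will be used to assess perioperative major adverse clinical events (MACE) rates". Section 3.3 likewise admits patients cannulated within 72 hours to the primary analysis.

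For early-arm patients who miss 72 hours, Patient Number in Section 1.0 says each "will be followed as a late-access subject" for 30 days after first cannulation. The matching visit table is headed "Schedule of Assessments (SoA) Late Access and Early Access Drop-outs".

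**The concern.** The late arm is the only concurrent randomised comparator for 30-day MACE. Section 4 frames an expectation about the two arms in the language of a significance test, and Section 9 rules out a test and offers no estimate in its place. Two separate exact intervals do not show how large an early-access excess remains compatible with the data. In a report written to this plan, two overlapping intervals could be read as confirming the expectation when they show little either way.

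The second issue is the denominator. If the early-access MACE rate can be taken either in everyone randomised to early access or only in those cannulated in time, the headline safety rate depends on a choice that is not fixed in advance in an open-label trial.

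**Working it through.** **Inputs.** Expected MACE 20%, no arm-specific rates (Section 4). Fifty early patients cannulated within 72 hours and 25 late (Section 9.1). Up to 10 early-arm misses (Section 6.8). No loss to follow-up projected at 30 days (Section 9.1). About 80% of the early arm cannulated in time (Section 4), which gives 50/0.80 = 62.5 randomised, or 12 to 13 misses. That is broadly in line with up to 10, since 50/60 = 83%. There is no power, alpha or margin to reproduce.

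**What the plan would print at 20% per arm (Clopper-Pearson 95%).**
- Early 10/50: 10.0% to 33.7%. With 10 misses kept as randomised, 12/60: 10.8% to 32.3%.
- Late 5/25: 6.8% to 40.7%.

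**What it would not print: early minus late.** Newcombe's interval uses the Wilson limits (l, u) of each arm, with arm 1 early and arm 2 late:
- lower = d − √[(p1 − l1)² + (u2 − p2)²]
- upper = d + √[(u1 − p1)² + (p2 − l2)²]

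Wilson limits: 10/50, 0.1124 to 0.3304; 12/60, 0.1183 to 0.3178; 5/25, 0.0886 to 0.3913. In every case d = 0.

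- 50 vs 25: lower = −√(0.0876² + 0.1913²) = −0.210; upper = √(0.1304² + 0.1114²) = +0.171.
- 60 vs 25: lower = −√(0.0817² + 0.1913²) = −0.208; upper = √(0.1178² + 0.1114²) = +0.162.

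The Miettinen-Nurminen method agrees closely: −21.1 to +17.6 points and −20.8 to +16.6 points.

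If replacing misses through the 2:1 randomisation plan also brought the late arm to about 30, 12/60 vs 6/30 gives a Newcombe interval of −19.1 to +15.8 points. The picture does not change.

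**Which groupings the documents support.**
- *As randomised, all implanted:* Section 9.2.2 with 9.2.7 and 10.2.8.
- *Misses excluded from the early group:* Data Populations in Section 1.0 for MACE, and Section 3.3 for the primary analysis. The sentence in 3.3 follows the effectiveness endpoint, so Section 1.0 carries most of the weight for MACE.
- Section 9.2.6 states that randomised patients are analysed as assigned, but the population table in Section 9.2.4 uses ITT only for baseline and disposition, so this does not settle safety.

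**Effect of the grouping.** Assumed counts: 10/50 among those cannulated in time, 5/25 late, and m events among 10 misses.

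| m | As randomised: (10+m)/60 − 5/25 | Newcombe 95% CI | Misses excluded: 10/50 − 5/25 |
|---|---|---|---|
| 0 | 16.7% − 20.0% = −3.3 | −23.8 to +12.6 | 0 |
| 2 | 20.0% − 20.0% = 0 | −20.8 to +16.2 | 0 |
| 4 | 23.3% − 20.0% = +3.3 | −17.8 to +19.8 | 0 |

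**The case against.** The strongest reply is that the trial never set out to compare arms. Its objective is acceptable rates, the size is openly logistical, testing is openly ruled out, and the Section 4 line is labelled an expectation rather than a success criterion. Anyone can compute the difference from the reported counts. Much of this stands: the absence of a test and the sample size are declared choices and are not faulted here. What remains is that the plan states an expectation about the difference between arms and specifies no quantity by which to judge it.

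A second reply is that the MACE window opens at first cannulation, within 72 hours of surgery in the early group and at day 10 or later in the late group. Early post-surgical events therefore fall inside one window and mostly outside the other, and a difference mixes this with any effect of early access. That also stands, and must be said beside the estimate. It applies equally to two rates printed side by side.

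A reader might go further and infer that misses would be analysed in the late group, so that the same data could give differences of opposite sign. The documents do not support that. The Patient Number text and the visit schedule govern follow-up, and no passage assigns misses to the late group for analysis. Of the two groupings that are supported, one gives exactly zero in the illustration, so neither reverses the other.

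**Conclusion.** The point holds in two parts. First, the Section 4 expectation cannot be assessed by anything planned in Section 9. At 20% in each arm, the data would leave open an early-access excess of about 16 to 17 points, almost as large as the expected rate itself. Second, Section 1.0 (with Section 3.3) and Section 9 define the early-access population differently, affecting up to 10 patients, or 12 to 13 at the expected 80% success. The effect is modest: up to 3.3 points either way in the illustration, against an interval roughly 38 points wide.

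These figures assume the protocol's 20% in both arms, complete 30-day data and, for the grouping effect, illustrative counts of 0 to 4 events among 10 misses. They do not show that the sample size is wrong or that a test is required. The correction should be made because it is nearly free and bears on what can be concluded on the primary safety endpoint.

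**What to change.** 1. In Section 9.2.2, state that MACE is analysed in the Safety Analysis Set grouped as randomised. Align Data Populations in Section 1.0 and the primary-analysis sentence in Section 3.3 with this. The within-72-hour subset may appear as a supplementary row. State that the Patient Number text and the drop-out visit schedule govern follow-up only.
2. Add the early-minus-late difference in the proportion of patients with at least one 30-day MACE, with a Newcombe 95% interval and no test. Note beside it that the window starts at first cannulation and so covers different post-implant periods in the two arms. State how implanted patients who are never cannulated, and so have no Day 0, are counted.
3. In Section 4, replace the phrase about significance with a descriptive expectation (rates, component types, and the difference with its interval) and state the precision shown above.

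The cost is wording in Sections 1.0, 3.3, 4 and 9.2.2 and one table row. It needs no extra patients, visits or data, and the descriptive design is kept. The drawbacks are that the interval will be visibly wide and that the contrast describes assignment to early access rather than early access received.

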9.2.3 Estimating patency rates and time to catheter removal

If possible, the estimated patency rates will be calculated using the SVS reporting standards guidelines.³¹ Kaplan-Meier (KM) survival curves will be used to estimate patency.

In figures, the numbers of patients at risk at the start of each interval (periodically for the KM) must be included and the standard error for each estimate of patency must be displayed with bars. When the standard error of the patency rate estimate exceeds 10%, the curve either should not be drawn or should be represented with a dotted line as a means of indicating lack of reliability of the estimate. If warranted, Cox hazard regression analysis may be performed where major risk factors identified during screening/baseline compromise the explanatory variables.

Time to catheter removal will be analyzed using the KM and/or Cox hazard regression as described above.

Artegraft, Inc. Version 4.0 21June2019
Protocol: ARTCT.BEACH.001 CONFIDENTIAL Page 44 of 81

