- Mahajan et al.²⁵also published an abstract describing initial results related to early access of Artegraft with the desire to minimize the time a patient would require the use of a tunneled hemodialysis catheter. In the period from November 2013 through October 2015 Mahajan implanted 58 patients with Artegraft. Of these 58 patients, 24 (41%) underwent early access, defined as access in less than 7 days. Seventeen (29%) of these patients had successful access on postoperative day 1, one underwent access on day 4, and six underwent access on day 7. Primary and secondary patency at 30 days was 90% and 96%, respectively. There was no early graft infection, thrombosis, or bleeding. He concluded that early access of the BCA graft is an alternative in patients with disadvantaged veins and in patients who require revisions of a native fistula due to bleeding and aneurysmal degeneration, thus eliminating the need for a temporary tunneled catheter in this patient population.
- Abdoli presented the work of his colleagues (Mahajan et al. ²⁶) on early Artegraft access at the 31st Western Vascular Society Meeting in 2016. In this study 36 grafts were subject to early access, defined as access within seven days. Twenty-one (58%) patients were cannulated within one day. At 180 days, primary patency was 44% and secondary patency was 80%. No difference was

Artegraft, Inc.
Protocol: ARTCT.BEACH.001

Version 4.0 CONFIDENTIAL

- observed in primary and secondary patency with grafts subjected to early or standard access time. Early access resulted in an overall complication rate of 17%, whereas standard cannulation resulted in an overall complication rate of 22%.

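### Patency precision is shown by a standard error that is zero until the first graft loss, and no interval method is named for patency

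*Combined protocol and SAP*

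**What the plan says.** Section 9.2.3 gives the estimator: "Kaplan-Meier (KM) survival curves will be used to estimate patency". For the figures it requires that "the numbers of patients at risk at the start of each interval (periodically for the KM) must be included" and that "the standard error for each estimate of patency must be displayed with bars". It then sets a reliability rule: "When the standard error of the patency rate estimate exceeds 10%, the curve either should not be drawn"; a dotted line is the permitted alternative.

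Section 9.1 makes a general promise: "Confidence intervals will be presented around each endpoint". It gives no method or confidence level for patency. Section 9.2.2 does name a method, for primary effectiveness and for MACE, where the percentage is to be reported "together with its 95% CI calculated using the Clopper-Pearson exact method". Section 9.2.3 has no equivalent sentence and no rule for a curve without events.

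The expected rates are in the objectives and endpoints table of section 4.0. They are minimum values: primary patency 85%, 75% and 65% at 30 days, 3 months and 6 months; primary-assisted patency 85% at all three times; secondary patency 90% at 3 and 6 months. No 30-day figure is given for secondary patency. The two groups are expected to be alike at 30 days on all three patency types.

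**The concern.** An SE bar is a poor picture of uncertainty when an estimate is at or close to 100% in a small group, and a bar of zero length reads as certainty. The same SE also drives the reliability flag, so the flag is silent exactly where the bar is misleading. Sections 9.1 and 9.2.1 plan description only, with no hypothesis test, so a reader will judge patency from the plotted curves, their bars and whatever interval accompanies them. If the interval is built from the same SE, for want of a named method, it too has zero width when no graft has been lost.

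**Working it through.** The plan states no SE or interval for patency, so there is no figure of its own to reproduce.

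**Inputs.** Late-access n = 25 and early-access n = 50 (section 9.1). Expected minimum rates of 65% to 90% (section 4.0). Published 30-day secondary patency after early access: 94% in the 70-patient poster and 96% in the related abstract (section 3.2: "Primary and secondary patency at 30 days was 90% and 96%, respectively").

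**Assumptions.** The SE formula is not named, so I take Greenwood's. With nobody censored before the time point it equals sqrt(p(1 − p)/n). Follow-up is taken as complete unless stated.

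1. **No losses.** With p = 1 the SE is sqrt(1 × 0/n) = 0 at any n. The Clopper-Pearson 95% lower limit for n of n is 0.025^(1/n):
   - 25 of 25: 0.025^(1/25) = 86.3%
   - 50 of 50: 0.025^(1/50) = 92.9%

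   Censoring does not change the zero: if no graft has been lost, the SE is 0 however few patients remain at risk.

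2. **One loss in 25.** The estimate is 96% and the SE is sqrt(0.96 × 0.04/25) = 3.9%. A bar of one SE each way runs from 92.1% to 99.9%; the exact 95% interval is 79.6% to 99.9%.

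3. **Can the 10% flag fire?** The SE is largest at p = 0.5. For n = 25 it is bounded by 0.5/sqrt(25) = 10.0%, which does not exceed 10%. For n = 50 the bound is 0.5/sqrt(50) = 7.1%. Without censoring, neither full-size group can be flagged at any patency rate.

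4. **How likely is a zero SE?** P(no loss in n) = p^n.

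| True patency | n = 25 | n = 50 | SE at n = 25 |
|---|---|---|---|
| 65% | 0.002% | <0.001% | 9.5% |
| 75% | 0.08% | <0.001% | 8.7% |
| 85% | 1.7% | 0.03% | 7.1% |
| 90% | 7.2% | 0.5% | 6.0% |
| 94% | 21% | 4.5% | 4.7% |
| 96% | 36% | 13% | 3.9% |

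The first four rows are the plan's minimum rates; the last two are the published 30-day secondary rates. Applying those two to the late group relies on the plan's expectation that the groups are alike at 30 days. Every curve also has zero SE from its start to its first loss, whatever its later level.

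**The case against.** Four points on the other side have force.

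- **Expected rates.** A reader might infer that the plan expects patency near 100%. It does not. Its minimum rates are 65% to 90%, where a no-loss result in 25 has at most a 7.2% chance and SE bars at n = 25 are 6.0% to 9.5%. The 100% entries in the section 3.2 patency table (assisted at 3 and 6 months, secondary at 3 months) are literature values. The same section also reports secondary patency of 89% at 6 months and 80% at 180 days. The problem is therefore confined to 30-day secondary patency and the early part of each curve.
- **Other measures of precision.** A reader might infer that the SE is the only one. Section 9.1 promises confidence intervals, and section 9.2.3 requires numbers at risk, so small numbers are visible. What is missing is the interval method. Nor does the plan say that intervals are the estimate ± 1.96 SE, so poor coverage of that interval cannot be charged to it.
- **Omitting a curve.** A reader might infer that the 10% rule removes the late-access comparator. The plan offers a dotted line as the alternative, the rule governs figures and not tables, and at the 30-day primary minimum of 85% the effective number would have to fall to 12 of 25 before the SE passed 10% (0.85 × 0.15/0.01 = 12.75). Section 9.1 projects no loss to follow-up at 30 days.
- **Reporting standard.** The plan follows the SVS reporting standards for patency. That source is not available here, so its display conventions cannot be judged; this is a reason to keep the SE in the tables.

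These points narrow the concern but do not remove it. Numbers at risk do not supply an interval, and the rule as written still draws 25 of 25 without error and as reliable.

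**Conclusion.** The concern holds in a limited form and is minor. Followed literally, section 9.2.3 gives zero-length bars and an unflagged curve for 25 of 25, where the exact 95% lower limit is 86.3%. Its 10% flag cannot act on 25 uncensored patients at any rate. The situation is unlikely at the plan's minimum rates (at most 7.2% in 25) but realistic for late-group 30-day secondary patency (21-36% at the published 94-96%) and certain for the opening stretch of every curve. The interval promised in section 9.1 would resolve it, but only if its method is valid with zero losses, and none is named.

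This rests on the Greenwood SE, complete follow-up to the time point, and carrying published early-access rates over to the late group. No sample size, error rate or success criterion depends on it, and the primary endpoints already have exact intervals.

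**What to change.** In section 9.2.3, report and plot for each patency estimate a 95% confidence interval that stays valid with zero losses:

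- Clopper-Pearson at the time point when nobody has been censored earlier;
- under censoring, the beta product confidence procedure, or a log-log interval with an exact fallback when there are no losses.

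Keep the SE in the tables for the SVS format. Always draw both arms, and use the dotted line the plan already allows in place of leaving a curve out.

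The cost is a few sentences in the plan and a few lines of code, with no change to conduct or sample size. The downside is that intervals near 100% become visibly wider.
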